2.3.5.2 PK/PD safety population

Pharmacokinetic/pharmacodynamic (PK/PD safety) population: all patients included in the PK population and having at least the baseline and one post-baseline ECG assessment.

2.4 STATISTICAL METHODS

2.4.1 Demographics and baseline characteristics

Continuous data will be summarized using the number of available data, mean, standard deviation (SD), median, minimum, and maximum for each treatment group. Categorical and ordinal data will be summarized using the number and percentage of patients in each treatment group.

Parameters described in [Section 2.1.2](#) will be summarized on the randomized population and the PK/PD efficacy population, analyzed in the treatment group to which they were randomized and overall treatment groups. Analyses for the safety population will be included in the appendices if the size of the safety population is different ($>10\%$) from the size of that in the primary analysis population for any treatment group.

P-values on demographic and baseline characteristic data will not be calculated.

Summary of baseline clinical signs/symptoms related to uncomplicated malaria and other relevant signs of malaria (Fever, Dizziness, Headache, Nausea, Anorexia, Vomiting, Diarrhea, Itching, Urticaria, Skin Rash, Abdominal Pain, Joint Pain, Muscle Pain, Palpitations, Sleep Problems, Confusion, Hearing Problems, Vision Problems, and Fatigue) by treatment arm.

No specific description of the safety parameters will be provided at baseline. If relevant, the baseline values will be described along with each safety analysis.

No specific description of the efficacy parameters will be provided at baseline. If relevant, the baseline values will be described along with each efficacy analysis.

2.4.2 Prior and concomitant medications

Prior and concomitant medications will be presented for the safety population. All medications taken within 2 months prior the screening visit, and during the study until the end of the study (Day 28), are to be reported in the e-CRF pages.

Medications will be summarized by treatment group according to the WHO-DD dictionary, considering the first digit of the anatomic category (ATC) class (anatomic category) and the first 3 digits of the ATC class (therapeutic category). All ATC codes corresponding to a medication will be summarized, and patients will be counted once in each ATC category (anatomic or therapeutic) linked to the medication. Therefore patients may be counted several times for the same medication.

The tables for prior, concomitant medications other than anti-malarial treatments and tables for concomitant anti-malarial treatments will be sorted by decreasing frequency of ATC followed by all other therapeutic classes based on the incidence across all groups. In case of equal frequency regarding ATCs (anatomic or therapeutic categories or standardized medications), alphabetical order will be used.

Patients will be counted once in each ATC level linked to the medication, therefore patients may be counted several times for the same medication. The numbers and percentages of patients in each level will be presented by treatment group.

2.4.3 Extent of investigational medicinal product exposure

The extent of IMP exposure will be assessed and summarized by actual treatment group, overall, using the safety population (Section 2.3.3).

IPs being given as single dose, exposure will be assessed by descriptive summaries of information collected at the time of administration in dedicated eCRFs pages, such as fasting status, total/partial administration and reason for partial administration, occurrence and timing of vomiting, for initial administration of FQ and OZ, and if any, for OZ re-dosing.

Duration of administrations will be also summarized descriptively as quantitative variables (number, mean, SD, median, Q1, Q3, minimum, and maximum) using:

- time between FQ and OZ administration: defined as the start date and time of OZ intake minus start date and time of FQ intake. Not defined in case FQ would be given after OZ.

- duration of OZ administration, for initial administration and, if any, for redose separately: defined as the end date and time of OZ intake minus start date and time of OZ intake.
- overall administration duration for initial administration: defined as the end date and time of OZ intake (initial administration) minus start date and time of FQ intake. Not defined in case FQ would be given after OZ.

Duration of IMP exposure will be summarized categorically by numbers and percentages of patients within each of the following categories:

- Ferroquine (FQ)
 - FQ not administered
 - Partial drug administered
 - All drug administered
 - Reason for not all drug administered (like adverse event, patient request, physician's decision and other reasons)
- Artefenomel (OZ439)
 - OZ439 not administered
 - Partial drug administered
 - All drug administered
 - Reason for not all drug administered (like adverse event, patient request, physician's decision and other reasons)
- Vomiting
 - No
 - Yes
 - After FQ administration, but before OZ439 administration
 - < 5 minutes after start of OZ439 administration
 - 5 – 35 minutes after start of OZ439 administration
 - > 35 minutes after start of OZ439 administration (*but not reported as vomiting since vomiting occurred more than 6 hours after dosing*)
- Re-dose of Artefenomel (OZ439)
 - No
 - Yes
 - OZ439 not administered
 - All drug administered
 - Reason for not all drug administered (like adverse event, patient request, physician's decision and other reasons)
- Vomiting following re-dose of Artefenomel
 - No
 - Yes
 - < 35 minutes after start of OZ439 administration

- > 35 minutes after start of OZ439 administration (*but not reported as vomiting since vomiting occurred more than 6 hours*)

Exploratory analyses studying the relationship between vomiting occurring less than 6 hours from IP start and potential explanatory variables such as baseline parasitaemia level, baseline body temperature, age, center, FQ formulation, durations of administration may be also performed if deemed relevant.

2.4.3.1 Extent of investigational medicinal product exposure

Not applicable (single-dose).

2.4.3.2 Compliance

Compliance is defined as taking the randomized treatment (both OZ439 and FQ) in full. Cases of overdose (defined as at least twice the intended dose within the intended therapeutic interval, adjusted according to the tested drug) will constitute AESI (serious or non-serious) if symptomatic and will be listed as such. Asymptomatic overdose has to be reported as a standard AE. More generally, dosing irregularities will be listed in Section 2.2.1.

2.4.3.3 Batch number and randomization scheme

The listing of patients receiving IMP from specified batch will also be provided by treatment arm and patient.

Besides, a listing sorted by site will be provided to display the randomization scheme (block number, sequence order with block, treatment arm, date and time of treatment allocation) of the study.

2.4.4 Analyses of efficacy endpoints

The primary analysis detailed in [Section 2.4.4.1.1](#) will be carried out on the PK/PD efficacy population.

All statistical analyses on secondary efficacy endpoints as well as on [Section 2.4.4.1.2](#) and [Section 2.4.4.1.3](#) will be performed on the mITT population only, unless otherwise stated.

2.4.4.1 Analysis of primary efficacy endpoint

2.4.4.1.1 Logistic regression on exposure-response for PCR-corrected ACPR

The exposure-response of single-dose OZ439/FQ for PCR-corrected ACPR at Day 28 will be analyzed using a logistic regression with the probability of a response in PCR-corrected ACPR at Day 28. The following exposure variables will be evaluated: OZ439 AUC₀₋₂₈ and

SSR97213 AUC_{0-Day28}

Baseline parasitemia (in log₁₀) and age (in years) will be tested as covariates. If needed, some other covariates like sex, weight (in kg), country or site will be tested in the model. The selection of the best fitted model will be done by calculating the fit statistics like AIC, BIC among all tested models, based on the choice of the predictor variables. The best model detected with the fit statistic chosen by the statistician will be specified in a footnote of the summary table.

The Wald test will be used to test the OZ439 exposure effect on PCR-corrected ACPR at Day 28.

This model will be run utilizing SAS® PROC LOGISTIC or similar using the outcome (response) binary variable (0/1) and the exposure variables (AUC for OZ439, AUC_{0-Day28} for FQ and SSR97213).

Results of logistic regressions of PCR-corrected ACPR on AUCs parameters of OZ439, FQ and SSR97213 will be provided in a summary table including odds ratio estimates, the corresponding 95% Wald confidence intervals (CI) and p-value for each compound and covariates.

Handling of dropouts or missing data

Patients not classified as failure for ACPR and with missing information on parasitemia at day 28 will be imputed following the criteria defined in [Section 2.1.4 \(Time points and imputation rules\)](#) or otherwise will be excluded from the analysis per protocol deviation.

Exposure-response will be done with and without vomiters if relevant.

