Evaluable participants are defined as all randomized participants with parasitologically confirmed malaria at baseline, who received the single administration of investigational medicinal product (IMP) and having parasitemia data post-randomization (Section 10.2).

Treatment groups and duration:

Study will last for up to 32 days for each participant:

- Up to 1 day screening period before the single-dose treatment
- 5 days of post-treatment surveillance, including 2 to 4 days hospitalization
- 24±2 days follow-up

Study treatments

Study treatments include FQ (all participants including arm A), OZ439 + FQ (participants of study arms B, C, and D), and a rescue therapy (all participants).

IMP: FQ (SSR97193)

- Formulation: 100 mg capsules
- Route of administration: oral
- Dose regimen: single dose of 400 mg given before OZ439

IMP: Artefenomel (OZ439)

- Formulation: sachet of 300 mg, 400 mg, and 600 mg of OZ439-alpha tocopherol polyethylene glycol 1000 succinate (TPGS) formulation + sachet of sucrose
- Route of administration: oral
- Dose regimen: single dose given after FQ, depending on the treatment arm: 0 mg for arm A, 300 mg for arm B, 600 mg for arm C, and 1000 mg for arm D

Noninvestigational medicinal products: rescue therapy

- A rescue treatment will be systematically administered at Day 28 for participants who reach Day 28 without having received a rescue medication
- The use of established anti-malarial drug combination per WHO recommendations and per local regulations and the choice of the best therapeutic option is left at investigator's decision.

Statistical considerations:

• **Primary analysis:** Logistic regression with p: probability of a response in PCR-corrected ACPR at Day 28 and OZ439 AUC and FQ AUC_{0-Day28} (SSR97213 AUC_{0-Day28} will be considered also) and baseline parasitemia as covariates will be fitted. The Wald test will be used to test the OZ439 exposure effect on PCR-corrected ACPR at Day 28.

Analysis of secondary endpoints:

Dose effect analysis:

A generalized multiple comparison procedures-modeling (MCP-Mod) approach will be used with PCR-corrected and crude ACPR at Day 28. Both linear and log model will be fitted. Then the dose response signal will be tested via contrasts based on dose-response shape.

Clearance rate estimation according to worldwide antimalarial resistance network (WWARN) (1).

- Other activity endpoints:

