10.3.1 Efficacy analyses

All efficacy analyses will be performed on the mITT Population. The efficacy analyses are summarized in Table 8.

Table 8 - Efficacy analyses

Endpoint	Statistical Analysis Methods
 	Otatistical Arialysis methods
For primary objective:Day 28 PCR-corrected ACPR	 The exposure-response association of single-dose OZ439/FQ for PCR-corrected ACPR at Day 28 will demonstrate how the probability of a response in PCR-corrected ACPR at Day 28 increases with exposure (AUC) to OZ439/FQ. Logistic regression with p: probability of PCR-corrected ACPR at Day 28 and OZ439 AUC and FQ AUC_{0-Day28} (SSR97213 AUC_{0-Day28} will be considered also) and baseline parasitemia as covariates will be fitted.
	 Results of logistic regressions of PCR-corrected ACPR on exposure will be provided in a summary table including odds ratio estimates, the corresponding 95% Wald CIs and p-value.
	 Frequency table for Day 28 PCR-corrected ACPR, i.e. proportion, percentage and exact binomial 95% CIs (two-sided by using Clopper-Pearson method for calculating binomial CIs) by treatment arm, will also be provided.
For secondary objectives:	
 Day 28 PCR-corrected ACPR 	 The dose-response exposure-response association of single-dose OZ439/FQ for PCR-corrected ACPR at Day 28 will demonstrate how the probability of a response in PCR-corrected ACPR at Day 28 increases with increasing dose of OZ439/FQ thanks to a logistic regression. Results of logistic regressions of PCR-corrected ACPR on dose will be provided in a summary table including odds ratio estimates, the corresponding 95% Wald Cls, and p-value.
 Parasitemia at baseline then every 6 h during the first 36 h then at 48 h and every 24 h until Day 7 	 Descriptive statistics (number of observations [n], mean, geometric mean, standard deviation [SD], median, first quartile [Q1], third quartile [Q3], minimum, and maximum) for parasitemia data (number of parasites/µL) (raw data and absolute change from baseline) will be displayed at each post-baseline assessment. Time profile plots (Mean ± standard error of the mean) of parasitemia will be provided for each treatment arm, one curve per arm.
Day 28 crude ACPR	 Same analysis using Clopper-Pearson method as for PCR-corrected ACPR will be done on crude ACPR at Day 28. The exposure-response (respectively dose- response) association of single-dose OZ439/FQ for crude ACPR will also be evaluated.

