	A generalized MCP-Mod approach will be used with PCR-corrected and crude ACPR at Day 28. Both linear and log model will be fitted. Then the dose response signal will be tested via contrasts based on dose-response shape. Selection of the model needs investigations which will be detailed in the SAP.

13-Nov-2017 Version number: 1

	served PRR at 24 h, h, and 72 h	•	Descriptive statistics (n, mean, geometric mean, standard deviation, median, Q1, Q3, minimum, and maximum) by treatment arm and time of measurement.
• Pa	rasite clearance rate	•	Parasite clearance estimator established by WWARN (1) will be used to identify the lag phase, clean the data for outliers, and determine the best model (linear, quadratic, cuboidal) to fit the log-transformed parasite data and afterward calculate the following estimate: the parasite clearance rate. Descriptive statistics (median, first Q1, Q3, minimum, and maximum) will be provided for each treatment arm.
• Tin	ne	•	Kaplan-Meier estimators.
-	to parasite clearance	•	For each variable, an overall overview including number of events (frequency and %), 25%, median and 75% quantile with 95% CI (expressed in weeks), cumulative
-	to 99% parasite reduction		incidence of events with 95% CI will be provided in a summary table for all participants.
-	to recrudescence or re-infection	•	Survival curves will be plotted by representing each treatment arm for all participants.
-	elapsed below LOQ of parasitemia	•	Cox model will be used for time to event endpoints with OZ439 doses and parasitemia at baseline as covariates, potential interaction will be explored.
Exploratory		Will be d	escribed in the statistical analysis plan finalized before database lock

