1.5 MODIFICATIONS TO THE STATISTICAL SECTION OF THE PROTOCOL

The statistical section of the protocol was never changed in an amendment.
There are no planned interim analyses.

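### SAP 2.4.4.1.1 lets the data choose the covariates of the primary exposure-response model, by a fit statistic not named in advance, where the protocol fixed them

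*SAP*

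**What the plan says.** **Protocol.** The synopsis describes a logistic regression in which OZ439 AUC, FQ AUC0-Day28 "and baseline parasitemia as covariates will be fitted. The Wald test will be used to test the OZ439 exposure effect". Table 8 in section 10.3.1 repeats the model: "and baseline parasitemia as covariates will be fitted". The only term left open is SSR97213 AUC0-Day28, which is to be considered as well. Neither place mentions age, sex, weight, country, site or a selection step. The power simulation in Appendix 8 likewise analysed every trial with one fixed model: both drugs' Day 7 exposures plus baseline parasitemia.

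**SAP 2.4.4.1.1.** Logistic regression, the OZ439, FQ and SSR97213 exposures and the Wald test on OZ439 are kept. The adjustment is not fixed. Baseline log10 parasitemia "and age (in years) will be tested as covariates" and, if needed, "some other covariates like sex, weight (in kg), country or site will be tested in the model". The best-fitting model is found with statistics of which AIC and BIC are given as examples, "among all tested models, based on the choice of the predictor variables". Then: "The best model detected with the fit statistic chosen by the statistician will be specified in a footnote of the summary table".

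**SAP 2.4.4.2.1.1** (crude ACPR, dose-response) uses nearly the same selection sentence and adds a parenthesis contrasting separate with combined AUC.

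**Declared changes.** SAP 1.5 states: "The statistical section of the protocol was never changed in an amendment". SAP 1.6 lists the new primary population, the added per-protocol population, fever clearance time, time to 50% reduction, the reporting of concentration/parasitemia work, the dropped half-life and the clarified efficacy baseline. It lists nothing about covariates or model selection.

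**The concern.** The primary objective is to show that OZ439 contributes to the combination, and the evidence is one Wald p-value from this regression. Under the protocol that p-value comes from a model known in advance. Under the SAP, three things are open: whether parasitemia stays (protocol 5.4 calls it a strong covariate), which other covariates join it, and which criterion decides. By the parallel wording in 2.4.4.2.1.1, the form of the exposure terms may be open too.

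AIC and BIC are functions of the Day 28 outcomes, so the reported model cannot be known until those outcomes are used. The SAP's closing summary of analyses lists no supportive analysis for this endpoint, so nothing guarantees that the protocol's model is reported at all. A reader of the report could not tell whether the odds ratio would have looked different under another equally permitted choice.

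**Working it through.** **1. The plan's own figure.** Inputs from Appendix 8: intercept 3.23, coefficients 0.12 (FQ), 0.73 (OZ439) and -1.27 (log10 parasitemia); log10 parasitemia normal with mean 4 and SD 0.55, truncated to 3.48-5.5; arm success rates 72%, 81%, 91% and 97%; 30 per arm; two-sided 5% Wald test. The concentration variances are not given. Assumed: log-normal, FQ CV 0.3 or 0.5, OZ439 CV 0.5, 0.8 or 1.1, correlation 0.2, medians calibrated to the four arm rates. Over 5,000 trials per setting, power is 85.3% to 92.4%, and three of the six settings (88.6%, 89.4%, 91.1%) lie within two points of 90%. The stated figure of around 90% is reproduced, for a fixed model.

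**2. Information available.** Expected failures = 30 × (0.28 + 0.19 + 0.09 + 0.03) = 30 × 0.59 = 17.7. Failures per slope:
- protocol model, three terms: 17.7 / 3 = 5.9
- with SSR97213 and age added, five terms: 17.7 / 5 = 3.5
- with sex and weight as well, seven terms: 17.7 / 7 = 2.5

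**3. Why the criterion matters.** For one extra covariate, AIC keeps it when the likelihood-ratio statistic exceeds 2; BIC keeps it when the statistic exceeds ln(120) = 4.79. Any covariate with a statistic between 2 and 4.79 is in under one and out under the other.

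**4. Selection simulated.** Same coefficients, exposures recalibrated to the arm rates, 30 per arm. Main run: 3,000 trials per scenario, baseline capped at the eligibility limit of 50,000/µL. Assumed: OZ439 CV 0.6 or 1.0, FQ CV 0.35, FQ-OZ439 log-correlation 0.3, SSR97213-FQ log-correlation 0.8, no true effect of age, sex or weight. Exposures are forced in; parasitemia and age are optional.

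| Result | AIC | BIC |
|---|---|---|
| Parasitemia dropped, baseline capped at 50,000/µL | 48-50% | 76-80% |
| Parasitemia dropped, baseline up to 10^5.5/µL as in Appendix 8 | 33-34% | 61-62% |
| Parasitemia-only adjustment (the protocol's) chosen, capped | 41-43% | 21-23% |
| Power (fixed protocol model 0.889-0.911) | 0.892-0.913 | 0.891-0.911 |
| Type I error (fixed protocol model 3.3-3.4%) | 3.7-3.8% | 3.6-3.7% |

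With the cap, AIC and BIC choose different models in 37-39% of trials, or 55-56% if sex and weight are candidates too. Where they differ, the OZ439 log-odds coefficient moves by a median of 6% (90th percentile 16-17%) and the p-value by a factor of 1.2 (90th percentile 1.6-1.7). The 5% verdict differs between them in 1-2% of trials, or 2-3% with sex and weight added.

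**5. How far discretion could go.** A second null simulation (2,000 trials per setting, overall response 72% or 85%) used wider candidate sets in which FQ and SSR97213 could also be dropped. False positives were 3.9-4.1% for the fixed model, 4.5-4.9% for AIC and 4.2-4.7% for BIC. Reporting the most favourable model gave 7.0-7.3% out of 16 models and 8.7-9.1% out of 128. Another 16-model set gave about 6%, against 4.4% for the fixed model.

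**The case against.** **The protocol section is only a summary.** Section 10.3 says so, and says the SAP will be finalized before database lock. But what it hands to the SAP is the analysis populations and the handling of missing, unused and spurious data, not the primary covariate set. Where the protocol defers model choice it says so, in the MCP-Mod dose-response text: "Selection of the model needs investigations which will be detailed in the SAP".

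**The search may concern exposure, not covariates.** The parenthesis in SAP 2.4.4.2.1.1 supports reading the choice of predictors as separate versus combined AUC. That is fair, and the simulation does not cover it. The covariates are still only tested, so the point stands and the open territory may be wider.

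**The practical effect is small.** This stands. The fitted model is also disclosed in a footnote.

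Four stronger readings are tempting, and the documents do not support them:
- That the SAP replaces the primary analysis. Endpoint, logistic regression, exposures and Wald test remain; what changes is how the adjustment is fixed.
- That SSR97213 or FQ may be dropped. The section says the model is run with both and reports an odds ratio for each compound. On SSR97213 the SAP is firmer than the protocol; only the form of the term is unclear.
- That the criterion is picked after the results are seen. The documents do not say when it is picked, and an open-label design does not show that the statistician has seen outcomes. Only the selected model is necessarily data-dependent.
- That type I error is inflated. Mechanical AIC or BIC selection does not show this.

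**Conclusion.** The point holds as a loss of prespecification in the primary analysis, undeclared in SAP 1.6. The textual conflict needs no assumption. Its size does: AIC and BIC differ in about 37-39% of trials with two candidate covariates, and parasitemia is dropped in about one third to one half of trials by AIC and about 61-80% by BIC, depending on how high baseline parasitemia is simulated. These rates rest on assumed concentration variances and correlations, on a candidate list that the SAP leaves open, and on all four arms being analysed. (SAP 2.3.5.1 asks for samples of both drugs, while OZ439 is not measured in arm A; without arm A, expected failures would be 30 × 0.31 = 9.3. That is a separate question.)

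Under either criterion applied mechanically, false positives stay at or below 5%, power is unchanged and the conclusion seldom moves. Only reporting the most favourable model would raise false positives, to about 6-9% depending on the candidate set. That is an upper bound on discretion, not a prediction. The change should be made because it removes that discretion cheaply, not because the result is shown to be unsafe.

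**What to change.** Before database lock, amend SAP 2.4.4.1.1 and 1.6:
- Name one primary model with OZ439 AUC, FQ AUC0-Day28 and log10 baseline parasitemia all forced in, tested by the two-sided 5% Wald test.
- State the form in which SSR97213 AUC0-Day28 enters: as a separate term or combined with FQ.
- Make adjustment for age, sex, weight, country and site, and any AIC- or BIC-selected model, sensitivity analyses under one named criterion.
- Record any remaining departure from the protocol model in SAP 1.6.

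The cost is SAP wording only. Patients, visits, sample size and the planned test do not change.
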